7 TREATMENT PLAN

This is a randomized, controlled, open label pilot trial. A total of 60 patients

will be enrolled, with at least 15 patients allocated to each treatment group (Arms C and D constituting the same treatment group). The initial treatment period is 6 months (24 weeks). During the initial treatment period, patients will be randomized to one of 4 arms: HCQ alone (Arm A), EVE alone (Arm B), combination HCQ and EVE (Arm C) – Arm C is closing to accrual with Amendment 7 – or control/delayed combination HCQ and EVE (Arm D). Starting with Amendment 7, patients who would have been allocated to Arm C will be redirected to Arm D in order to increase the number of patients with repeat DTC assessments to aid assay reproducibility analysis. At the conclusion of 3 cycles of therapy (Arms A, B, and C) or 3 cycles of observation (Arm D), patients will undergo repeat bone marrow aspirate. Patients on Arm D will then commence combination therapy with HCQ + EVE for 6 cycles (24 weeks). After 3 cycles of therapy, patients on Arm D will undergo another bone marrow aspirate. After 6 cycles of therapy, patients on all arms will undergo another bone marrow aspirate. Patients with a negative bone marrow aspirate for DTCs at after cycle 6 will have all therapy discontinued and enter the follow up phase. Patients who have persistently positive bone marrow DTCs will be continued on combination HCQ + EVE for an additional 6 cycles (24 weeks). At the conclusion of this combination treatment period (cycle 12), all treatment will be discontinued and a bone marrow aspirate will be performed.

Patients will be evaluated at the initiation of every cycle for adverse events, and dose reductions will be employed for toxicity. Patients will continue to be followed for recurrence events for 3 years after completion of treatment.

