7.1 Study Arms

Patients will be randomized during the Screening Phase to one of four investigational arms. These are shown in the schema above and detailed as follows (Note that Arm C is closing with Amendment 7):

Arm A: Patients will receive HCQ, 600 mg BID, for 24 weeks. If they are determined to have detectable DTCs after week 24, they will be crossed over to combination therapy, in which they will continue HCQ, 600 mg BID and add EVE, 10 mg daily for an additional 24 weeks.

Arm B: Patients will receive EVE, 10 mg daily, for 24 weeks. If they are determined to have detectable DTCs after week 24, they will be crossed over to combination therapy, in which they will continue EVE, 10 mg daily and add HCQ, 600 mg BID, for an additional 24 weeks.

Arm C: Patients will receive the combination of HCQ, 600 mg BID, and EVE, 10 mg daily, for 24 weeks. If they are determined to have detectable DTCs after week 24, they will continue combination HCQ/EVE therapy for an additional 24 weeks. Arm C is closing with Amendment 7. Patients randomized after Amendment 7 who would have been assigned to Arm C will be redirected to Arm D.

Arm D: Patients will be observed for 12 weeks without study therapy. At the completion of the observation period, they will receive combination therapy of HCQ, 600 mg BID and EVE, 10 mg daily for 24 weeks. If they are determined to have detectable DTCs after week 24, they will continue combination HCQ/EVE therapy for an additional 24 weeks.

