7.2 Drug Administration

Patients will be randomized to receive HCQ, EVE, the combination, or observation (control)/delayed combination. A “cycle” is 28 days (4 weeks) in duration. Both agents will be given continuously (28 of 28 days), without break, unless necessary due to toxicity. Patients will initially be treated on the assigned arm for 6 cycles (24 weeks), or observed for 3 cycles (Arm D), followed by delayed treatment on the combination. At that point, patients who are persistently positive for bone marrow DTCs will be allowed to crossover as outlined in the study schema and below. The crossover therapy will be given for 6 cycles (24 weeks) as well. Because EVE and HCQ are oral medications, pill counts and treatment diaries will be used to monitor adherence to therapy. Patients are required to bring the pill bottles and treatment diaries to each visit.

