#### Bayesian Poisson regression model

The number of DTCs observed by visit for each patient was analyzed with a Bayesian Poisson regression model that included treatment-by-visit effects and patient-level random intercepts to account for overdispersion in the outcomes. We denote observations within index  $i \in 1, ..., N$  and patients with index  $s[i] \in 1, ..., S$ . Let  $y_i$  represent the number of DTCs for observation i. The Bayesian model is specified as follows:

$$y_i \sim Pois(\lambda_i)$$
  
 $\log(\lambda_i) = \alpha + \mu_{s[i]} + X'_i \beta$ 

where  $\alpha$  is an overall intercept,  $\mu_{s[i]}$  is a patient-level intercept,  $X_i$  is a vector of treatment by visit effects, and  $\beta$  is a vector of treatment effects by visit. The following non-informative prior distributions are specified on the unknown model parameters:

$$\alpha \sim N(0, 10^2)$$
  
 $\beta_j \sim N(0, 10^2), j = 1:j$   
 $\mu_s \sim N(0, \sigma^2), s = 1:S$   
 $\sigma \sim t_3^+(0, 1)$ 

Posterior sampling was done using the *brms* package (version 2.19.0) in the R programming language (version 4.3.1). Treatment effects for HCQ, EVE, and HCQ + EVE are presented by visit as the percent reduction in mean DTCs compared to observation alone at C3. Combination effects are evaluated by comparing the mean number of DTCs with HCQ + EVE to HCQ and EVE alone by visit. The estimated probability of DTC clearance is presented by visit and treatment group. Summaries of model parameters include the posterior mean, median, standard deviation (SD), and 95% credible interval (CrI).

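### The SAP measures C6 drug effects against observation that ends at week 12, and does not say how Arm D's on-treatment marrows enter the HCQ + EVE group

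*SAP*

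**What the plan says.** **SAP, Bayesian Poisson regression model.** The data are described so: "The number of DTCs observed by visit for each patient was analyzed with a Bayesian Poisson regression model". The model "included treatment-by-visit effects and patient-level random intercepts to account for overdispersion in the outcomes"; it lists no separate term for time since entry. Treatment effects "are presented by visit as the percent reduction in mean DTCs compared to observation alone at C3", so one cell is the reference for every visit. For the incremental benefit of the combination: "Combination effects are evaluated by comparing the mean number of DTCs with HCQ + EVE to HCQ and EVE alone by visit". The available SAP text does not say which cell Arm D's marrows enter once that arm starts treatment.

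**Protocol 7.1, Arm D.** "Patients will be observed for 12 weeks without study therapy". After that "they will receive combination therapy of HCQ, 600 mg BID and EVE, 10 mg daily for 24 weeks".

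**Protocol 5.3 and 7.** Marrows are scheduled after three and six cycles of therapy in every arm, with an additional one at the end of Arm D's observation. Section 7 describes Arms C "and D constituting the same treatment group". From Amendment 7, patients who would have gone to Arm C go to Arm D.

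**Protocol 2.2.2 and 12.2.2.** The no-treatment comparison in 2.2.2 is set at 3 months. The 6-month regression in 12.2.2 compares the active treatments with the delayed-treatment group, which by then has had three cycles of HCQ + EVE. Neither section provides an untreated marrow at 6 months.

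**The concern.** A controlled effect needs treated and untreated patients measured at the same time since entry. That holds at C3 for the single agents. It cannot hold at C6, because nobody is untreated at week 24. The SAP still expresses C6 results as a reduction against observation, without stating the assumption this requires.

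The second issue is conditional. If Arm D's treated marrows count as HCQ + EVE by cycle of therapy, the combination is compared with each single agent at the same visit label but at different times since entry. Arm D also supplies the whole observation cell, so part of HCQ + EVE versus observation becomes a before-after comparison within the same patients. Arm D's share of the combination group grows after Amendment 7.

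A continuing trend is possible: Protocol 7.3 keeps patients with hormone receptor positive disease on endocrine therapy throughout. The documents give neither its size nor its direction. At stake are the reduction in DTCs and the incremental benefit of the combination, both secondary efficacy endpoints meant to inform a larger trial.

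**Working it through.** The plan states no figure to reproduce here; the question is what each contrast estimates.

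**Step 1: nominal weeks since entry.** Protocol 7.2 says a cycle "is 28 days (4 weeks) in duration", so 3 cycles = 12 weeks and 6 cycles = 24 weeks. Arm D starts treatment after 12 weeks.

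| Cell | Week since entry |
|---|---|
| Observation, C3 (Arm D) | 12 |
| Arms A, B, C at C3 | 12 |
| Arms A, B, C at C6 | 24 |
| Arm D, after 3 cycles of therapy | 12 + 12 = 24 |
| Arm D, after 6 cycles of therapy | 12 + 24 = 36 |

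C6 in Arms A to C is 12 weeks later than its reference; Arm D's C6 is 24 weeks later.

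**Step 2: closed form with no drug effect.** Let r be the ratio of untreated mean DTCs over each 12 weeks. It is assumed, with range 0.8 to 1.1. With entry mean m, the reference is m·r. Pool Arms C and D 15/15 (weights 0.5 and 0.5, also assumed).

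- Single agent at C3: r/r = 1, no bias.
- Single agent at C6: r²/r = r, so the false reduction is 1 − r.
- HCQ + EVE at C3: (0.5r + 0.5r²)/r = 0.5(1 + r).
- HCQ + EVE at C6: (0.5r² + 0.5r³)/r = 0.5r(1 + r).
- Combination versus single agent, at C3 or C6: 0.5(1 + r).

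| False reduction | r = 0.8 | r = 0.9 | r = 1.0 | r = 1.1 |
|---|---|---|---|---|
| Single agent, C6 | 20% | 10% | 0 | −10% |
| HCQ + EVE, C3 | 10% | 5% | 0 | −5% |
| HCQ + EVE, C6 | 28% | 14.5% | 0 | −15.5% |
| Combination v single agent | 10% | 5% | 0 | −5% |

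The single-agent C6 row does not depend on how Arm D is coded. The other rows assume pooling by cycle.

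**Step 3: check in the SAP's model form.** Poisson counts, treatment-by-visit cells and a normal patient intercept were simulated with no drug effect and fitted by maximum likelihood, not with the SAP's priors. Assumed: median patient mean of 2 at baseline, intercept SD 1, 15 per arm, 1,200 runs per setting; figures are from median estimates.

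| False reduction, r = 0.8 | Arm D treated marrows pooled | Left out |
|---|---|---|
| HCQ v observation, C3 | 6.3% | −1.5% |
| HCQ v observation, C6 | 24.5% | 19.1% |
| HCQ + EVE v observation, C3 | 15.0% | 0.2% |
| HCQ + EVE v observation, C6 | 32.2% | 18.2% |
| HCQ + EVE v HCQ, C3 | 8.1% | 0.5% |
| HCQ + EVE v HCQ, C6 | 8.8% | −0.2% |

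At r = 1.0 with pooling, all are within 3% of zero. With an assumed C/D split of 8/22 at r = 0.8, the combination appears about 13% better than HCQ at both visits. Under pooling, HCQ + EVE at C3 exceeds the closed-form 10% because the patient intercept gives weight to Arm D's within-patient change, which is 1 − r = 20%.

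So coding can repair the C3 and combination contrasts. It cannot repair C6 versus observation.

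**Step 4: would change from baseline be safer at C6?** At r = 0.8 it shows a false reduction of 1 − 0.8² = 36%, against 20% for the SAP's single-agent contrast. Baseline is also selected positive. With Poisson counts at patient rate λ and entry requiring at least one cell, the false fall from baseline with no trend is E[λe^(−λ)]/E[λ]. For log-SD 1 this is about 6.4% at median rate 2 and 43.5% at median rate 0.3 (assumed values). Under the same selection, week 24 versus week 12 differs by about 0, because both are repeat marrows in patients selected alike.

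**The case against.** The strongest case against has four parts.

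- **Pooling is not documented.** A reader might infer that the SAP labels Arm D's delayed treatment by cycle and merges it with Arm C. The SAP does not say so, and part of it is not available for review. Section 7 of the protocol makes C and D one group when describing allocation, and 12.2.1 permits combining them for feasibility only. This stands: pooling is the natural reading, but the second half of the point must remain conditional. Likewise, how far Arm D drives the combination estimate depends on a C/D split that the documents do not give.
- **Selection does not create the C6 bias.** A reader might infer that entry on a positive marrow makes C6 look better. Step 4 shows that it does not; the observation marrow absorbs that regression. A trend continuing after week 12 is needed. This stands. Protocol 12.2.2 does anticipate at most a 4% response rate without treatment, but that concerns individual responses arising from variability in DTC measurement, and does not exclude a trend in the mean.
- **Alignment by cycle is defensible.** It matches exposure, and indexing by week alone would set three cycles in Arm D beside six cycles of a single agent. This stands as a reason to show both, not to leave the coding unstated.
- **The design cannot do more.** The control is openly a delayed-treatment group, and the SAP names its reference. True, but this limits what can be claimed at C6. It does not make the contrast concurrent.

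**Conclusion.** The point holds for C6 on the SAP's text and the protocol's schedule: every C6 reduction against observation is non-concurrent and equals a drug effect only with no untreated trend after week 12. For HCQ + EVE at C3 and the contrasts with single agents, it holds only if Arm D's treated marrows are pooled by cycle. Single-agent C3 contrasts are concurrent by design; under pooling the simulation moved HCQ at C3 by 6.3% at r = 0.8, through the shared patient intercept.

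The sizes above are illustrations under an assumed r and assumed splits. The documents do not support saying that the reported effects are biased by a given amount, or that the bias favours the drugs. They support saying that the plan cannot separate drug from time at C6 and does not state the assumption it needs. Severity is should-fix: the contrasts are secondary in a pilot whose primary endpoint is feasibility.

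**What to change.** 1. Make week 12 (C3), Arms A, B and C versus Arm D as randomised, the only controlled claim against observation.
2. State how Arm D's on-treatment marrows are coded, and give them their own cells.
3. Report HCQ + EVE, and its contrasts with HCQ and with EVE, from Arm C alone as well as from C and D pooled.
4. Add a sensitivity analysis with a time-since-entry term. After week 12, such a term can be separated from treatment only by assuming that the combination acts alike at the same cycle in Arms C and D; say so.
5. Keep C6 versus observation at C3 only if it is labelled non-concurrent and its no-trend assumption is stated.
6. Do not substitute change from baseline as evidence of effect. Report it as descriptive, because baseline is selected positive.

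The cost is SAP wording and a re-run; no new data are needed. The Arm C-only combination estimate uses fewer patients, so its interval will be wider.
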